5.5 PHARMACOKINETIC , PHARMACODYNAMIC, AND PHARMACOGENOMIC/PHARMACOGENETIC ANALYSES

Population pharmacokinetic (PK) and pharmacokinetic/pharmacodynamic (PK/PD) analysis are specified in the protocol but will not be discussed in this SAP. Separate analysis plan(s) for these analyses will be developed and finalized before the database lock.

5.5.1 Pharmacokinetic Analyses

Not Applicable.

5.5.2 Pharmacodynamic Analyses

Not Applicable.

5.5.3 Pharmacogenomic/Pharmacogenetic Analyses

Not Applicable.

5.6 SAFETY ANALYSES

All safety analyses will be performed on the Safety Analysis Set. Unless specified, all safety assessments will be summarized both overall (regardless of baseline platelet count) and within each baseline platelet count cohort. Safety data, presented by treatment group, will be summarized on an “as treated” basis using descriptive statistics or frequency count.

Study Day 1 for all safety analyses is defined as the date of the first dose of study drug. Unless specified otherwise, the baseline value will be defined as the most recent value reported prior to the first dose of study drug.

5.6.1 Extent of Exposure

The extent of exposure to study drug will be characterized by duration of exposure (in days) for each treatment group.

Duration of exposure will be defined as the number of days between the date the subject received the first dose of study drug and the date the subject received the last dose of study drug, inclusive. Duration of exposure will be summarized using descriptive statistics by treatment group. In addition, the duration of exposure will be categorized, and will be summarized using frequency count by treatment group.

5.6.2 Adverse Events

The AE verbatim descriptions (investigator terms from the CRF) will be classified into standardized medical terminology using the Medical Dictionary for Regulatory Activities (MedDRA). Adverse events will be coded to the MedDRA (Version 15.1 or higher) lower level term (LLT) closest to the verbatim term. The linked MedDRA preferred term (PT) and primary system organ class (SOC) will also be captured in the database.

A treatment-emergent AE (TEAE) is defined as an AE that

- Emerged during treatment (up to 30 days after the last dose of study drug), having been absent at pretreatment (Baseline) or
- Reemerged during treatment (up to 30 days after the last dose of study drug), having been present at pretreatment (Baseline) but stopped before the last dose of study drug plus 30 days, or
- Worsened in severity during treatment (up to 30 days after the last dose of study drug) relative to the pretreatment state, when the AE was continuous.

Only those AEs that are treatment emergent will be included in summary tables. All AEs, treatment emergent or otherwise, will be presented in subject data listings.

An overview table of TEAE, including number of subjects with TEAEs, treatment-emergent serious adverse events (SAEs), deaths, severe TEAEs, study drug related TEAEs, TEAEs leading to study drug withdrawal will be provided. In addition, the following summaries will be produced:

- Incidence of TEAEs by SOC and PT
- Incidence of treatment-related TEAEs by SOC and PT
- Incidence of procedure-related TEAEs by SOC and PT
- Incidence of TEAEs after procedure (with an onset date on or after Procedure Day) by SOC and PT
- Incidence of TEAEs related to platelet transfusion complications by SOC and PT
- Incidence of TEAEs by SOC, PT, and common terminology criteria for adverse events (CTCAE) grade
- Incidence of treatment-related TEAEs by SOC, PT, and CTCAE grade
- Incidence of TEAEs by SOC, PT, and relationship to treatment

If a subject experiences more than one TEAE within a preferred term, the subject will be counted only once in the calculation of incidence of TEAE within that preferred term. Similarly, if a subject experiences more than one TEAE within a SOC, the subject will be counted only once in the calculation of incidence of TEAE within that SOC. If a subject experiences more than one TEAE within a preferred term (or SOC), the occurrence with the highest CTCAE grade will be used in the calculation of the incidence of TEAE within that preferred term (SOC) by CTCAE grade. If a subject experiences more than one TEAE within a preferred term (or SOC), the occurrence considered most closely related to study drug will be used in the calculation of the incidence of TEAE with that preferred term (SOC) by relationship (given by investigator).

The following summaries will also be presented for the treatment-emergent SAEs:

- Incidence of treatment-emergent SAEs by SOC and PT
- Incidence of treatment-related treatment-emergent SAEs by SOC and PT

- Incidence of treatment-emergent SAEs by SOC, PT, and relationship to treatment.

In addition, number (percentage) of subjects with TEAEs and treatment-related TEAEs leading to discontinuation from study treatment will also be summarized by MedDRA SOC, PT for each treatment group.

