Patient treatment decisions are guided by platelet count measurements, as well as by clinical judgment on the risk of bleeding. Patients with moderate to severe thrombocytopenia ( $<50 \times 10^9/L$ ) associated with liver disease are commonly administered platelet transfusions immediately prior to elective diagnostic or therapeutic procedures in order to mitigate the risk of bleeding. The extent of the bleeding risk relates to the degree of thrombocytopenia, the extent of other coexisting coagulopathy(ies), and the type of elective procedure. While temporarily effective, platelet transfusion therapy can have significant health and economic consequences, including the development of refractoriness to subsequent platelet transfusions, potential transmission of infectious agents, transfusion reactions, and, in rare cases, fatality. Unfortunately, in patients requiring repeated platelet transfusions, both the magnitude of the platelet increase and the duration of that increase declines with increasing numbers of transfusions. This refractoriness to treatment can pose a major challenge for patients undergoing procedures in preparation for liver transplant or other procedures pertinent to their care. For patients who have acquired refractoriness to platelet transfusion, an unintended consequence is often the need to delay or even cancel important procedures. Additionally, like all blood products, platelets are a precious commodity with a limited shelf life. Approximately 9 million units of platelets are transfused each year in the US; 40% in surgical settings. Liver disease patients are believed to represent a significant proportion of the patient population regularly receiving platelet transfusions. A recent assessment at the University of Colorado Denver Medical School revealed that up to 20% of all platelet transfusions were given to liver disease patients.

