#### 9.1.2.3 Procedure Day (Visit 4)

This will occur 5 to 8 days after the last dose of study drug (on Study Day 10 to 13).

All Procedure Day assessments are to be completed prior to the procedure and include assessments shown in [Section 9.5.2.1 \(Table 5\)](#).

In addition, all subjects are required to return study drug and the dosing diary at this visit.

The elective procedure for those subjects whose preprocedural platelet count is  $>200 \times 10^9/L$  on Visit 4 (Procedure Day) may be delayed at the discretion of the investigator until platelet counts are below  $200 \times 10^9/L$ . All subjects whose platelet count exceeds  $200 \times 10^9/L$  will be required to have a Doppler assessment at Visit 5. For any subjects where the presence of a PVT is suspected, confirmation of diagnosis, via CT scan or MRI, should be performed and treatment for PVT initiated per local guidelines.

Permitted procedures and the risk of bleeding associated with each procedure are listed in [Table 1](#). It is planned that no fewer than 10% of subjects will be enrolled into the high risk group and no more than 60% of subjects in the low-risk group.

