### 9.3.3 Removal of Subjects From Therapy or Assessment

The investigator may withdraw the subject from the study at any time for safety or administrative reasons. The subject may stop study drug or withdraw from the study at any time for any reason. A subject who discontinues study treatment, but does not withdraw consent, should be followed for subsequent protocol-specified visits and procedures.

In these subjects, the Visit 4 (Procedure Day) assessments for the study will be performed as an end of study visit as outlined in [Section 9.5.2.1 \(Table 5\)](#), with the exception of the elective procedure, which may take place outside the study. The primary reason for discontinuation and all other reason(s) contributing to the subject's discontinuation from study drug should be collected on the Subject Disposition CRF page.

These subjects will also be required to complete a follow-up visit, Visit 6 (Day 35) assessments, which will be conducted approximately 30 days after the last dose of study drug.

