8 DEFINITIONS AND CONVENTIONS FOR DATA HANDLING

8.1 VISIT WINDOW

Study Day 1 is defined as the date of the first dose of study drug. The analysis visits defined below will be used in the by-visit summaries:

Visit	Target Visit Date	Visit Window	Analysis Visit
Visit 2 (Baseline)	Study Day 1	Less or equal to Study Day 1	Last visit on or before Study Day 1
Visit 3	Study Day 4	Study Day 2 to 7	Closest visit to Study Day 4
Visit 4	Study Day	Subjects with procedure:	Subjects with platelet

Visit	Target Visit Date	Visit Window	Analysis Visit
(Procedure Day)	10 to 13	Study Day 8 to actual procedure day Subjects without procedure: Study Day 8 to 13	transfusion: last visit before transfusion Subjects with procedure but without transfusion: last visit before procedure Subjects without platelet transfusion or procedure: closest visit to Study Day 10
Visit 5	7 Days post procedure	Subjects with procedure: 1 to 10 days post actual procedure day Subjects without procedure: Study Day 14 to 20	Subjects with procedure: visit closest to 7 days post actual procedure day Subjects without procedure: closest visit to Study Day 17
Visit 6	Study Day 35	Subjects with procedure: Greater or equal to actual procedure day +11 days Subject without procedure: Greater or equal to Study Day 21	Closest visit to Study Day 35

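### The SAP table of TEAEs after procedure starts at Procedure Day, the name of Visit 4, so as written it can include TEAEs that precede the procedure or occur without one (minor)

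*SAP*

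**What the plan says.** Among the adverse event summaries in SAP 5.6.2 is "Incidence of TEAEs after procedure (with an onset date on or after Procedure Day) by SOC and PT". The rule uses dates only and includes the day itself. It mentions neither the time of the procedure nor whether one took place. Under SAP 5.6 the table is run on the whole Safety Analysis Set.

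Protocol 9.1.2.3 treats Procedure Day as Visit 4 and sets the order of that day: "All Procedure Day assessments are to be completed prior to the procedure". The same section says that for a subject above 200 × 10^9/L at that visit the procedure "may be delayed at the discretion of the investigator until platelet counts are below" that level. It gives no upper limit on the delay.

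Visit 4 also exists for subjects who stop study drug early. Protocol 9.3.3 says: "In these subjects, the Visit 4 (Procedure Day) assessments for the study will be performed as an end of study visit". It leaves the elective procedure out of that visit. Note b to protocol Table 5 extends Visit 4 to anyone withdrawn early for any reason.

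The SAP 8.1 window for Visit 4 runs "Study Day 8 to actual procedure day" for subjects with a procedure and from Study Day 8 to 13 for subjects without one.

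**The concern.** The label promises events after the procedure, but the rule starts the clock at a visit. The two can differ in three ways.

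- **Same day, before the procedure.** Protocol 7.1 says that such patients are "commonly administered platelet transfusions immediately prior to elective diagnostic or therapeutic procedures". A reaction to platelets given that morning would be tabulated as post-procedural. Such reactions are expected more often on placebo, because the drug is meant to reduce transfusion.
- **Delay.** TEAEs between Visit 4 and a postponed procedure would be counted. Delay depends on a count above 200 × 10^9/L, so it should fall mainly on avatrombopag.
- **No procedure.** A subject with a Visit 4 but no procedure can contribute TEAEs to the table and stays in its denominator.

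At stake is the reading of the only adverse event summary in SAP 5.6.2 that is defined by timing relative to the procedure. The first two kinds of misplaced event are linked to treatment arm, so they need not cancel in the comparison.

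**Working it through.** The plan states no figure for this table, so there is none to reproduce. The check compares the passages and then does simple arithmetic on size.

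**Which date does the rule use?** Protocol 9.1.2.3 and SAP 3.2 attach the name Procedure Day to Visit 4, and both allow the procedure to be put off after that visit. SAP 8.1 needs a separate term for the real date, and SAP 5.6.2 does not use it. The natural reading is therefore Visit 4. The reading is not certain: the SAP 8.1 windows are stated to serve the by-visit summaries, and SAP 9 places derivation rules in separate documents.

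**Which parts depend on that reading?** The same-day part does not: a date-only, inclusive rule counts the whole calendar day whichever date is used. The delay and no-procedure parts do. With the actual procedure date as the start, both disappear.

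**Days miscounted in an affected subject.** A TEAE may start up to 30 days after the last dose, so the window ends at Day 5 + 30 = Day 35. The number of days counted is 35 − (Visit 4 day) + 1, and the number before the procedure is (procedure day) − (Visit 4 day). Day 15 is the upper end of the procedure window in the per-protocol criteria of SAP 5.2.1.

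| Visit 4 | Procedure | Days before procedure | Days counted | Share |
|---|---|---|---|---|
| Day 10 | Day 10 | 0 | 26 | 0% |
| Day 10 | Day 13 | 3 | 26 | 12% |
| Day 10 | Day 15 | 5 | 26 | 19% |
| Day 8 | Day 15 | 7 | 28 | 25% |

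These are shares of days within one subject, not shares of events in the trial.

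**How many subjects could be delayed for a high count?** Protocol 7.2.1 projects fewer than 2% above 200 × 10^9/L, and SAP 4 plans 133 avatrombopag subjects: 0.02 × 133 = 2.66. Delay is discretionary, so the number actually delayed may be lower.

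**How many had no procedure?** The documents give no number. SAP 5.2.1 foresees such subjects but removes them only from the per-protocol set.

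**Same-day reactions (illustration).** SAP 4 assumes response rates of 18% on placebo and 18% + 35% = 53% on avatrombopag. Non-response is 100% − 18% = 82% and 100% − 53% = 47%, a gap of 35 points. With an assumed same-day, pre-procedure reaction rate r among non-responders, equal in both arms, the difference is 0.35 × r.

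| Assumed r | Placebo | Avatrombopag | Difference |
|---|---|---|---|
| 1% | 0.82% | 0.47% | 0.35 points |
| 5% | 4.10% | 2.35% | 1.75 points |
| 10% | 8.20% | 4.70% | 3.50 points |

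Non-responders include subjects rescued after the procedure and subjects with missing outcomes, so 82% and 47% overstate the share transfused beforehand on the day. If the same fraction of non-responders in each arm was so transfused, the true difference is that fraction of the figures shown, and the table is an upper limit.

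**The case against.** The strongest reply is that the heading of the table shows its intent. A programmer may well use the actual procedure date, and the specifications that would settle this are not available here. SAP 8.1 also lets the Visit 4 record move: for a subject with a procedure and no transfusion it takes the last visit before the procedure. A repeat count after a delay could therefore become the Procedure Day record. This stands as a reason not to treat the delay and no-procedure parts as certain. It does not remove the same-day part, and it leaves the SAP text open to two readings.

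Second, the important signals are reported elsewhere. SAP 5.6.2 has separate tables for procedure-related TEAEs and for platelet transfusion complications. SAP 5.6.6.1 summarises thromboembolic events without regard to the procedure, and again by HCC status. All adverse events are listed by subject. This stands. A reader might infer that a thrombosis at peak count would be hidden, but the documents do not support that: only its place in this one table is in doubt.

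Third, including the day itself is a defensible convention when clock order is unknown, because it keeps same-day procedural complications in view. This also stands. The documents require times for transfusions, rescue procedures and local platelet samples, but do not say that adverse event onset times or procedure start times are collected. A remedy that depends on clock times may not be workable.

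**Conclusion.** The point holds as a minor one. As written, the onset rule does not match the label of the table and can place pre-procedure and no-procedure TEAEs under a post-procedure heading. The delay and no-procedure parts assume that Procedure Day means Visit 4, which is the documents' usual usage but is not confirmed for this table.

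The size cannot be derived from the documents. Delay for a high count touches fewer than about 2.7 of 133 avatrombopag subjects at the projected rate. The range of 0.35 to 3.5 points for same-day reactions rests on an assumed reaction rate, applied to every planned non-responder. A reader might infer that the table carries a known bias in favour of the drug. The documents support an expected direction for the same-day part only, not an amount. Misplaced events during a delay would tend the other way, because they would fall mainly on avatrombopag.

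No hypothesis test is planned for safety, and no efficacy result or all-subject TEAE summary is affected.

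**What to change.** Replace the bullet in SAP 5.6.2 with a definition based on the actual procedure date, the term already used in SAP 8.1:

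- Take numerator and denominator from Safety Analysis Set subjects who had the elective procedure. State whether a procedure done outside the study after discontinuation counts, since protocol 9.3.3 allows for one.
- Show TEAEs with onset on the procedure date in one row and those with later onset in another. Use clock times to order same-day events only if they were collected.

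The cost is one SAP sentence and a small programming change, on a date that SAP 8.1 already relies on. There are two downsides. Same-day events stay unordered where no times exist. The denominator also depends on something that happens after randomisation, so the table should be read as descriptive and not as a randomised comparison. The all-subject TEAE tables stay as they are.

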5.6.3 Laboratory Values

Laboratory results will be summarized using Système International (SI) units, as appropriate. With the exception of urinalysis, platelet function tests and platelet count (which is considered as an efficacy parameter), for all quantitative parameters listed in [protocol Section 9.5.1.5 Safety Assessments \(Laboratory Measurements\)](#), the actual value and the change from baseline will be summarized by visit and treatment group using descriptive statistics. Analysis of changes from baseline will be based on the number of subjects with both nonmissing baseline and relevant postbaseline results.

Laboratory test results will be assigned a low/normal/high (LNH) classification according to whether the value is below (L), within (N), or above (H) the laboratory parameter's reference range. Shifts from baseline (LNH) to Procedure Day and to the end of the Follow-up Phase will be presented for each laboratory parameter. Similar shift tables from baseline (LNH) to the highest/lowest postbaseline LNH classification will also be provided. A subject will be counted once in highest LNH classification and once in the lowest LNH classification.

The Sponsor's Grading for Laboratory Values (see [Appendix 1](#)) presents the criteria that will be used to identify subjects with treatment-emergent markedly abnormal laboratory values (TEMAV). Except for phosphate, a TEMAV is defined as a postbaseline value with an increase from baseline to a grade of 2 or higher. For phosphate, a TEMAV was defined as a postbaseline value with an increase from baseline to a grade of 3 or higher. When displaying the incidence of TEMAVs, each subject will be counted once in the laboratory parameter high and in the laboratory parameter low categories, as applicable.

5.6.4 Vital Signs

For each vital signs parameters (diastolic and systolic blood pressure, pulse, respiration rate, temperature and weight), the actual value and changes from baseline will be summarized by visit and treatment group using descriptive statistics. Analysis of changes from baseline will be based on the number of subjects with both nonmissing baseline and relevant postbaseline results.

5.6.5 Electrocardiograms

For each electrocardiogram (ECG) parameter (including PR interval, RR interval, QRS interval, QT interval, QTcB interval, QTcF interval and heart rate), the actual value and change from baseline will be summarized by visit and treatment group using descriptive statistics. ECG interpretation (categorized as normal and abnormal) will be summarized using frequency count at each visit by treatment group.

Maximum postbaseline QTcB and QTcF will also be tabulated by treatment group as follows:

- Number and percentage of subjects in the borderline (430-450 msec), abnormal category (> 450 msec), and highly abnormal (>500 msec) during the treatment, and
- Number and percentage of subjects with an increment of 30-60 msec and > 60 msec from the baseline visit.

QT will be corrected primarily using Fridericia's formula (QTcF) and also using Bazett's formula (QTcB) defined as:

- QTcF is the heart rate corrected QT interval by Fridericia's formula: $QTcF = QT/(RR)^{0.33}$
- QTcB is the heart rate corrected QT interval by Bazett's formula: $QTcB = QT/(RR)^{0.5}$.

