Abnormal laboratory values should not be listed as separate AEs if they are considered to be part of the clinical syndrome that is being reported as an AE. Any laboratory abnormality considered to constitute an AE should be reported on the Adverse Event CRF.

It is the responsibility of the investigator to review all laboratory findings in all subjects and determine if they constitute an AE. Medical and scientific judgment should be exercised in deciding whether an isolated laboratory abnormality should be classified as an AE.

Abnormal ECG (QTc, corrected for heart rate) results, if not otherwise considered part of a clinical symptom that is being reported as an AE, should be considered an AE if the QTc interval is  $>450$  ms and there is an increase of  $>60$  ms from baseline. Any ECG abnormality that the investigator considers as an AE should be reported as such.

All AEs must be followed for 30 days after the subject's last dose, or until resolution, whichever comes first.

**Every effort must be made by the investigator to categorize each AE according to its severity and its relationship to the study treatment.**

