### ELECTROCARDIOGRAMS

Descriptive statistics for ECG parameters and changes from baseline will be presented by visit and treatment group. ECG interpretation (categorized as normal; abnormal, not clinically

significant; and abnormal, clinically significant) will be presented by visit and treatment group using frequency count.

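### The absolute QTc categories in SAP 5.6.5 ignore baseline and no QTc shift table is planned, so new crossings of 450 or 500 msec cannot be separated from prolongation present before dosing

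*SAP*

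**What the plan says.** SAP 5.6.5 (Electrocardiograms) sets up one categorical QTc tabulation: "Maximum postbaseline QTcB and QTcF will also be tabulated by treatment group as follows". It has two parts.

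- Absolute categories: "Number and percentage of subjects in the borderline (430-450 msec), abnormal category (> 450 msec), and highly abnormal (>500 msec) during the treatment".
- Rises: "Number and percentage of subjects with an increment of 30-60 msec and > 60 msec from the baseline visit".

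The section also summarizes actual values and change from baseline for each ECG parameter, by visit and treatment group, and gives normal/abnormal interpretation counts at each visit. It plans no shift table for QTc or for interpretation.

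Baseline is already defined for all safety analyses: SAP 5.6 states that "the baseline value will be defined as the most recent value reported prior to the first dose of study drug". Protocol Table 5 schedules ECGs at Screening, Baseline, Visit 3 (Day 4) and Visit 6 (Day 35). Neither the inclusion nor the exclusion criteria (Protocol 9.3.1 and 9.3.2) limit QTc.

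Other safety rules refer to baseline. For laboratory data, SAP 5.6.3 says "a TEMAV is defined as a postbaseline value with an increase from baseline to a grade of 2 or higher" (grade 3 for phosphate), and it adds shift tables from baseline to the highest and lowest postbaseline class. SAP 5.6.2 counts an adverse event as treatment-emergent only if it is new, has returned or has worsened. Protocol 9.5.1.5 says an abnormal QTc result "should be considered an AE if the QTc interval is" above 450 ms and has also risen by more than 60 ms from baseline.

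**The concern.** The absolute rows mix two kinds of subject: those whose QTc was already above the threshold before dosing, and those who crossed it afterwards. Only the second kind says anything about the drug, yet both are reported as belonging to the treatment period. If a noticeable share of this population starts above 450 msec, most of the >450 row could be pre-existing. The expected difference between arms then shrinks, and chance imbalance in baseline prevalence adds noise to it. Safety data are read descriptively, without tests, so the reader relies on these counts being interpretable as they stand.

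**Working it through.** **What each row can show.** The documents state no QTc figure to reproduce, so the first check is to pass example subjects (baseline to maximum, msec) through the planned rules.

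| Subject | Rise | Absolute row | Increment row | Protocol AE rule |
|---|---|---|---|---|
| 440 to 505 | 65 | >450 and >500 | >60 | met |
| 445 to 470 | 25 | >450 | none | not met |
| 480 to 505 | 25 | >450 and >500 | none | not met |
| 460 to 462 | 2 | >450 | none | not met |

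The large rise is caught. The subject newly above 450 (445 to 470) looks exactly like the one who was there all along (460 to 462). The subject newly above 500 (480 to 505) likewise cannot be told from one already above 500 at baseline. Where the rise is 30 msec or more, an increment row records it but does not say whether a threshold was crossed: 380 to 415 and 440 to 475 are both +35 and fall in the same row.

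**How large the dilution could be.** Inputs:

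- Arm sizes: 133 and 67 (SAP 4).
- Share above 450 msec at baseline, *b*: not in the documents; assumed 5% to 30%, the same in both arms, and all assumed to stay above 450.
- New crossings among the rest, *q*: not in the documents; assumed 7% on avatrombopag and 2% on placebo.

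Proportion in the planned >450 row: *p* = *b* + (1 − *b*)*q*. The difference between arms is therefore (1 − *b*)(0.07 − 0.02).

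SE as planned: √[*p*A(1 − *p*A)/133 + *p*P(1 − *p*P)/67]. SE for new crossings: the same form with *q* in place of *p* and denominators 133(1 − *b*) and 67(1 − *b*).

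Worked for *b* = 10%:

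- *p*A = 0.10 + 0.90 × 0.07 = 0.163; *p*P = 0.10 + 0.90 × 0.02 = 0.118; difference 0.045.
- SE as planned = √(0.163 × 0.837/133 + 0.118 × 0.882/67) = 0.051.
- SE for new crossings = √(0.07 × 0.93/119.7 + 0.02 × 0.98/60.3) = 0.030, around a difference of 0.050.

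The chance that the observed difference is zero or negative comes from binomial simulation on the same inputs.

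| *b* | Planned row, A v P | Difference (points) | SE planned / new (points) | No excess seen: planned / new |
|---|---|---|---|---|
| 5% | 11.7% v 6.9% | 4.8 | 4.2 / 2.9 | 11% / 4% |
| 10% | 16.3% v 11.8% | 4.5 | 5.1 / 3.0 | 17% / 5% |
| 20% | 25.6% v 21.6% | 4.0 | 6.3 / 3.1 | 25% / 6% |
| 30% | 34.9% v 31.4% | 3.5 | 7.0 / 3.3 | 30% / 7% |

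The share of the avatrombopag >450 row that was there before dosing is *b*/*p*A: 0.05/0.1165 = 43% at the low end and 0.30/0.349 = 86% at the high end.

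SAP 5.6 also presents safety within each platelet cohort. At 67 v 33 with *b* from 10% to 30%, the chance of no visible excess is 29% to 37% as planned, against 12% to 15% for new crossings.

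With higher assumed rates (15% v 5%), a true ratio of 3.0 appears in the planned row as 1.97 at *b* = 5% (19.3% v 9.8%) and 1.21 at *b* = 30% (40.5% v 33.5%). The direction is kept.

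**The case against.** The strongest reply is that the absolute rows are only half of the QTc tabulation. The increment rows refer to baseline, are given by arm, and count every rise of 30 msec or more whatever the starting value. By-visit actual values and changes are shown too, so a baseline difference in mean QTc between arms would be visible. The combined protocol criterion already generates an adverse event, unless it is part of a syndrome reported as one, and treatment-emergent events are tabulated. Randomization balances pre-existing prolongation on average. QTc is not an event of special interest in SAP 5.6.6.1, dosing lasts five days, and no decision rule uses this table.

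All of that stands, and it rules out a stronger reading. A reader might infer that the plan as a whole would conceal new QTc prolongation on avatrombopag. The documents do not support this: larger rises are reported, and the effect on the absolute rows is dilution and noise, not a directional bias. Nor is the lack of a shift table unique to ECGs, since vital signs (SAP 5.6.4) have none either.

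A reader might also infer that SAP 5.6.5 wrongly dropped a category, because Protocol 9.7.1.8 lists three interpretation classes, ending "significant; and abnormal, clinically significant) will be presented by visit and treatment group", and the SAP has two. That is not established. SAP 7 records the category as updated for consistency with the eCRF and protocol, and the eCRF is not available to show what was collected.

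The reply does not reach the within-subject cross-classification. Mean changes do not identify individuals, and separate counts of level and of rise cannot be combined after the fact into a count of new crossings.

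**Conclusion.** The gap is real but narrow. The absolute QTc rows are not conditioned on baseline, new crossings of 450 or 500 msec cannot be read from any planned table, and those with a rise below 30 msec escape every baseline-referenced count. The figures above rest wholly on assumed prevalence, full persistence above 450 and assumed crossing rates. They show how the mechanism works and are not an estimate for this trial. They also treat the >450 row in isolation, whereas it would be read beside the increment rows, and nothing was computed for >500. This is a minor improvement to a descriptive safety table; it does not affect efficacy or any conclusion rule.

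**What to change.** In SAP 5.6.5, keep the existing rows and add, for QTcF and QTcB by treatment group:

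- a shift table of baseline category by maximum postbaseline category;
- new-onset counts for >450 and >500 msec, with subjects at or below that threshold at baseline as the denominator;
- optionally, a row for the protocol's own criterion (above 450 ms with a rise of more than 60 ms).

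Present ECG interpretation as a shift from baseline, in whatever categories the eCRF holds.

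The QTc additions use ECGs already scheduled and the baseline definition already in SAP 5.6. The cost is a few lines of SAP text, one extra table shell and slightly smaller denominators in the new-onset rows.
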